## **5.5 Definition and Handling of Loss to Follow-up**

If the investigator fails to contact the subject through multiple attempts of various methods (at least 3 telephone calls and 1 SMS/WeChat, and each attempt is not on the same day), the subject can be judged as lost to follow-up, and the corresponding contact records (contact person, contact information and specific time) should be maintained, and the date of the last contact should be considered as the date of the subject's early withdrawal.

## 6 Study Treatment

### 6.1 Investigational Products

In this study, the investigational products include the investigational drug (TJ0113 capsules) and the placebo.

	TJ0113 Capsules	Placebo
Active Ingredient	TJ0113	None
Dosage Form	Capsules	Capsules
Strength	100 mg	100 mg
Package Size	30 capsules/bottle	30 capsules/bottle
Description	Opaque rich yellow hard capsules, and with pale pink solid contents	Opaque rich yellow hard capsules, and with off-white solid contents
Storage Conditions	Protected from light, keep in tight container at 2°C - 8°C	Protected from light, keep in tight container at 2°C - 8°C
Provided by	Hangzhou Phecdam Co., Ltd.	
Method of Administration	Take orally on an empty stomach in the morning, once daily, and fast within half an hour after the administration. It can be taken together with the background medication for PD. It is recommended that subjects should take the drug at the same time $\pm$ 1 h each day as much as possible.	

### 6.2 Drug Storage

Both the investigational drug and the placebo will be provided free of charge by Hangzhou Phecdam Co., Ltd. and distributed to the study site as scheduled. The investigational drug should be kept and distributed by specially-assigned person in the clinical trial institution, and stored in a refrigerator at 2-8°C as required. Returned drugs (used, partially used or unused drugs, including empty packaging materials) must be kept separately from the drugs that are not dispensed.

### 6.3 Drug Dispensing

All investigational products will be randomized by the IWRS, and each subject will be assigned multiple drug numbers by visit during the study. The system will automatically record the drug allocation information of each subject, including the date of drug dispensing and drug number. The drug manager should dispense the drugs according to the drug number

assigned by the system at each visit.

#### **6.4 Drug Receipt, Record and Accountability**

The drugs will be administered at each site by the principal investigator or his or her authorized representative (e.g., pharmacist), i.e., the drug manager. The third-party transportation company designated by the sponsor will transport the drugs to each study site according to the transportation requirements of the drug. The drug manager will receive the drug after confirming that the packaging of the drug is intact and there is no temperature excursion, and ensure that all investigational drugs are safely stored according to relevant regulations and drug storage requirements. The quantity of received drugs, the date of receipt, the quantity used, the date of use, and the storage amounts will be recorded and counted accordingly, and the CRA should check and conduct accountability at each visit.

#### **6.5 Drug Return and Destruction**

All drugs will be returned by the investigator after the EOS or returned to the third-party drug destruction company designated by the sponsor in batches according to the actual situation of the site during the study. The company will carry out uniform destruction according to the corresponding regulations and requirements.

## 7 Treatment for Study Participants

### 7.1 Study Treatment

Subjects enrolled in this study will be randomized in a 1:1 ratio into two cohorts (Cohort 1: 200 mg dose group; Cohort 2: 400 mg dose group) based on a stratification factor whether they have been receiving levodopa, the background medication for PD (yes vs. no) at a stable dose. Within each cohort, the subjects will be randomized into the TJ0113 capsules group and the placebo group in a ratio of 2:1.

### 7.2 Concomitant Medication

All concomitant medications used during the study must be documented with indication and dose information (including dose, route of administration and dosing frequency), and start and stop dates of administration. Medications used prior to signing the ICF will be recorded as prior medications, and those used after signing the ICF will be recorded as concomitant medications. All concomitant medications should be documented in the subject's original medical record and the eCRF.

#### 7.2.1 Permitted Concomitant Medications/Therapies

Concomitant medications/therapies allowed to be administered from signing of the ICF to 1 week after the last dose of the investigational product include:

- Background medications for PD that have been stably used for at least 4 weeks before study entry, of which the treatment regimen can remain unchanged (for subjects who have used any background medications for PD including levodopa, if any AE such as dyskinesia occur, the dose of levodopa is allowed to be reduced at the discretion of the investigator);
- Other concomitant medication or therapies that have already been used at the time of screening, of which the original drug/therapy type, dose or treatment frequency and setting should remain unchanged as much as possible;
- Drugs required to be used for treating the AEs.

#### 7.2.2 Prohibited Concomitant Medications/Therapies

The following medications/therapies are prohibited during the period from signing the ICF until 1 week after the last dose of the investigational product:

- Any procedure/surgery that may affect the progression of PD, including but not

limited to brain surgery (such as stereotactic destruction and deep brain stimulation) or traditional Chinese medicine physiotherapy (such as acupuncture), etc.;

- Any drugs other than investigational product that may affect the progression of PD (excluding those which have been on a stable dose for PD at the time of study entry).
- Serotonin reuptake inhibitors (such as fluoxetine, paroxetine, trazodone, citalopram, escitalopram, etc.);
- Any unauthorized drugs (i.e., other investigational drugs that are currently tested in clinical trials and have not been approved for marketing).

The investigator will determine and record the use of any emergency medication, drug name, dose, route of administration, purpose of treatment, start and end date of administration.

If subjects have used any prohibited drug or non-drug therapy, it will be recorded as a protocol deviation. The investigator decides on whether the subjects will continue the follow-up or be withdrawn from the study based on the severity of the deviation and the subjects' condition

### **7.3 Compliance of Study Subjects**

During the study, the administration of both the investigational product and the background medication for PD will be recorded in the eCRF. Subjects' medication compliance will be calculated according to the quantity of investigational product dispensed and returned and combined with the diary card.

Calculation method for medication compliance: medication compliance = actual dose/planned dose \* 100%.

If the subject's compliance is between 80% and 120%, it means that the compliance is good; if the subject's compliance is < 80% or > 120%, it indicates poor compliance.

## 8 Endpoint-Related Assessment

### 8.1 Efficacy Assessment

#### 8.1.1 MDS-UPDRS

The MDS-UPDRS consists of four parts: Part I (Nonmotor Experiences of Daily Living), Part II (Motor Experiences of Daily Living), Part III (Motor Examination), and Part IV (Motor Complications). Throughout the study, each subject should have a fixed rater to evaluate his/her score using MDS-UPDRS.

- For subjects who have received the anti-PD drug at a stable dose for at least 4 weeks prior to study entry, the MDS-UPDRS assessment time points and corresponding assessment parts are as follows:

Visit	MDS-UPDRS assessment part	Assessment time points
V1	Part I	No special requirements
	Part III	Before administration of background medication for PD ( $\geq 12$ hours from the most recent dose of the background medication for PD)
V2, Early Withdrawal Visit (if applicable)	Part III	Before administration of background medication for PD ( $\geq 12$ hours from the most recent dose of the background medication for PD)
		After administration of background medication for PD (to be performed at $2 \pm 1$ hours after the administration of background medication for PD at this visit)
	Parts I, II, and IV	No special requirements
V3~V6	Part III	Before administration of the investigational product and the background medication for PD ( $\geq 12$ hours from the most recent administration of background medication for PD and the investigational product)
		After administration of the investigational product and the background medication for PD (to be performed at $2 \pm 1$ hours after the administration of the background medication for PD and the investigational product at this visit)
	Parts I, II, and IV	No special requirements

- For subjects who have not received the anti-PD drug at study entry, the MDS-UPDRS assessment time points and corresponding assessment parts are as follows:

Visit	MDS-UPDRS assessment part	Assessment time points
V1	Part I	No special requirements
	Part III	No special requirements
V2	Part III	No special requirements
	Parts I, II, and IV	No special requirements
V3~V6	Part III	Before administration of the investigational product ( $\geq 12$ hours from the most recent administration of the investigational product)
		After administration of the investigational product (to be performed at $2 \pm 1$ hours after the administration of the investigational product at this visit)
	Parts I, II, and IV	No special requirements
Early Withdrawal Visit (if applicable)	Part III	$\geq 12$ hours from the most recent administration of the investigational product
	Parts I, II, and IV	No special requirements

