## **8.7.2 Treatment Period**

### **8.7.2.1 V3 (D7, W1)**

At V3, the following procedures will be performed:

- Subjects must be fasted before each visit (fast for at least 10 hours overnight without depriving of water);
- Vital signs;
- Physical examination;
- 12-lead ECG;
- Laboratory tests: including hematology, blood chemistry, urinalysis, coagulation function test, and urine pregnancy test (only for women of childbearing potential);
- Weight measurement and Ccr calculation;
- Return diary card;
- MDS-UPDRS Part III score before administration of the investigational product and the background medication for PD (if applicable) ( $\geq 12$  hours from the most recent administration of background medication for PD (if applicable) and the investigational product);
- Dispense the drug using the Clinflash IRT system;
- Take investigational product and background medication for PD (if applicable) concomitantly;
- MDS-UPDRS Part III score after administration of the investigational product and the background medication for PD (if applicable) (to be performed at  $2 \pm 1$  hours after the administration);
- MDS-UPDRS Parts I, II, and IV scores;
- Record concomitant medications/therapies;

- Record AEs;
- Dispense a new diary card;
- Note:
  - At V4, subjects should return to the study site for a visit in the morning (recommended from 7:00 a.m. to 10:00 a.m.) with their diary cards and on an empty stomach (fast for at least 10 hours overnight without depriving of water);
  - If the subject has received stable medication for PD within at least 4 weeks prior to study entry, the administration of investigational product and last dose of the background medication for PD on the day before V4 should be at least 12 hours apart from the agreed visit time of V4, and the subject should bring background medication for PD (at least a single dose) that has been stably taken to the hospital on the day of V4, and take the first dose of such medication on the day of V4 under the guidance of the investigator.

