##### **11.4.2 Analysis for Primary Endpoint**

The primary objective of this study is to assess the efficacy of TJ0113 capsules in the treatment of patients with early-stage PD. The main concern of interest is the treatment difference in terms of the changes from baseline in the MDS-UPDRS Part III (motor examination) scores after 12 weeks of treatment between the TJ0113 capsules group and the placebo group.

Definition of estimand:

- Population: patients with early-stage PD
- Endpoint: changes from baseline in scores of MDS-UPDRS Part III (motor examination) after 12 weeks of treatment. Evaluation time point:  $\geq 12$  hours from the most recent dose of anti-PD drug.
- Treatment: treatments will be randomly assigned; subject will be randomized in a 1:1 ratio to two cohorts (200 mg dose group and 400 mg dose group); and within each cohort, the subjects will be randomized in a 2:1 ratio to the TJ0113 capsules group and the placebo group.
- Concomitant event and management strategy: For any concomitant medication (excluding the investigational product and stable anti-PD medications at the time of enrollment) or treatment that could potentially impact the PD disease process, a therapeutic strategy will be employed.
- Population-level summary: differences in the least square mean of the changes from baseline in MDS-UPDRS Part III (motor examination) scores after 12 weeks of treatment between the TJ0113 capsules group and the placebo group.

The analysis will be performed using a mixed models for repeated measures (MMRM) with the changes from baseline in the MDS-UPDRS Part III scores after 12 weeks of treatment as

the dependent variable, whether subjects have been receiving levodopa, the background medication for PD (yes vs. no) at a stable dose at baseline and the baseline MDS-UPDRS Part III score as the covariates, and the treatment group, visit, and the treatment group-by-visit interaction as the fixed effects.

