3.2. Efficacy Endpoints

MDS-UPDRS

The MDS-UPDRS consists of four parts: Part I (Nonmotor Experiences of Daily Living), Part II (Motor Experiences of Daily Living), Part III (Motor Examination), and Part IV (Motor Complications). Throughout the study, each subject should have a fixed rater to evaluate his/her score using MDS-UPDRS.

➤ For subjects who have received the anti-PD drug at a stable dose for at least 4 weeks prior to study entry, the MDS-UPDRS assessment time points and corresponding assessment parts are as follows:

Visit	MDS-UPDRS assessment part	Assessment time points
V1	Part I	No special requirements
	Part III	Before administration of background medication for PD (\geq 12 hours from the most recent dose of the background medication for PD)
V2, Early Withdrawal	Part III	Before administration of background medication for PD (\geq 12 hours from the most recent dose of the background

Visit (if applicable)		medication for PD)
		After administration of background medication for PD (to be performed at 2 ± 1 hours after the administration of background medication for PD at this visit)
		Parts I, II, and IV
V3~V6	Part III	Before administration of the investigational product and the background medication for PD (≥ 12 hours from the most recent administration of background medication for PD and the investigational product)
		After administration of the investigational product and the background medication for PD (to be performed at 2 ± 1 hours after the administration of the background medication for PD and the investigational product at this visit)
		Parts I, II, and IV

- For subjects who have not received the anti-PD drug at study entry, the MDS-UPDRS assessment time points and corresponding assessment parts are as follows:

Visit	MDS-UPDRS assessment part	Assessment time points
V1	Part I	No special requirements
	Part III	No special requirements
V2	Part III	No special requirements
	Parts I, II, and IV	No special requirements
V3~V6	Part III	Before administration of the investigational product (≥ 12 hours from the most recent administration of the investigational product)
		After administration of the investigational product (to be performed at 2 ± 1 hours after the administration of the investigational product at this visit)

Visit	MDS-UPDRS assessment part	Assessment time points
	Parts I, II, and IV	No special requirements

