6.10.1. Primary Efficacy Endpoint Analysis

The primary efficacy endpoint of this study is the change from baseline in the Movement Disorder Society-Unified Parkinson's Disease Rating Scale (MDS-UPDRS) Part III (Motor Examination) score after 12 weeks of treatment. Evaluation time point: ≥ 12 hours from the most recent dose of anti-PD drug. The statistical methods, strategies for concomitant events, and handling of missing values are summarized in the following table:

Analysis	Analysis Population	Statistical Analysis Methods	Strategies and Missing Data Handling
Primary Analysis	FAS	Mixed Model for Repeated Measures (MMRM)	Treatment strategy, no imputation for missing values
Sensitivity Analysis 1	FAS	Analysis of Covariance (ANCOVA)	Treatment strategy, LOCF for missing value imputation
Sensitivity Analysis 2	FAS	Mixed Model for Repeated Measures (MMRM)	Treatment strategy, MI for missing value imputation
Supplementary Analysis 1	PPS	Mixed Model for Repeated Measures (MMRM)	Treatment strategy, no imputation for missing values
Supplementary Analysis 2	FAS	Mixed Model for Repeated Measures (MMRM)	A hypothetical strategy of employing MI to impute missing data.

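### The Part III rating tables follow anti-PD drug status at entry, the primary endpoint follows the latest anti-PD dose, and the SAP has no timing check after baseline

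*Protocol*

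**What the plan says.** - **Endpoint** (Protocol 3.2 and 11.4.2; SAP 3.1 and 6.10.1): Part III is scored at least 12 "hours from the most recent dose of anti-PD drug". Entry status is not mentioned.
- **Table for patients unmedicated at entry** (Protocol 1.2 footnote 19 and 8.1.1, headed "For subjects who have not received the anti-PD drug at study entry, the MDS-UPDRS assessment time points and corresponding assessment parts are as follows"; SAP 3.2, headed "For subjects who have not received the anti-PD drug at study entry"): the pre-dose rating at V3 to V6, and the early-withdrawal rating, must be at least 12 "hours from the most recent administration of the investigational product". No interval from any anti-PD drug is set.
- **Table for patients on stable drug at entry**: the 12 hours run from background medication and the investigational product at V3 to V6, and from background medication alone at early withdrawal.
- **Permitted drugs** (Protocol 7.2.1): "Background medications for PD that have been stably used for at least 4 weeks before study entry".
- **Pre-visit notes** (Protocol 8.7): the notes for V3 and V4 open with a condition, "If the subject has received stable medication for PD within at least 4 weeks prior to study entry". The note for V5 and V6 drops that condition but still speaks only of background medication, where applicable.
- **New PD drugs** (Protocol 7.2.2): prohibited. Use is a deviation, after which "The investigator decides on whether the subjects will continue the follow-up or be withdrawn from the study".
- **Primary analysis** (SAP 6.10.1): MMRM on the FAS, "Treatment strategy, no imputation for missing values".
- **Timing rule for analysis values** (SAP 6.1): baseline Part III is matched to the correct interval from the last anti-PD dose. Nothing equivalent is stated for later visits.

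**The concern.** A patient who starts or adds an anti-PD drug after randomisation has no row of their own in the rating tables. Suppose a patient is untreated at entry, starts a drug in Week 6, and takes it shortly before the V6 pre-dose rating. The site has met its table, but the score reflects the acute effect of the new drug and is not an OFF score.

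The 12-hour interval is there to keep that acute effect out of the primary endpoint, and these are the patients for whom it matters most. If such scores enter the Week 12 comparison in unequal numbers by arm, the treatment difference moves. If they are noticed only at data review, the team must decide without a rule whether to keep or drop them. The same gap reaches the secondary Part III endpoints defined at 12 hours or more, and total scores 1, 3 and 5.

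**Working it through.** **Step 1. Endpoint against tables.** The plan states no figure to reproduce here, so this part is a comparison of text.

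| Patient at V3 to V6 | Endpoint requires 12 h from | Table requires 12 h from | Same? |
|---|---|---|---|
| Unmedicated throughout | no anti-PD drug to time from | investigational product | no conflict |
| Stable drug, nothing added | that drug | that drug and investigational product | yes |
| Unmedicated at entry, starts a drug | the new drug | investigational product only | no |
| Stable drug, adds a second | the later of the two | background medication and investigational product | not for the added drug |

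The last row depends on reading background medication as the pre-entry drug.

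**Step 2. Can such a score reach the primary analysis?** Protocol 7.2.2 allows continued follow-up. The strategy for such medication in Protocol 11.4.2 and SAP 3.1, read as treatment policy, keeps later data. SAP 6.10.1 applies it to the FAS without imputation. No post-baseline timing check intervenes. So it can.

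**Step 3. Would it be detected?** Protocol 7.2 asks for dose, route, frequency and start and stop dates of concomitant drugs, not the clock time of the last dose. Protocol 7.3 requires administration records for the investigational product and background medication. On this text, the interval for a newly started drug may not be recoverable.

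**Step 4. Size.** The documents give no start rate, no ON-OFF difference and no SD, so every input except the arm size is an assumption.

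- Arm size: 150 / 2 = 75 per cohort; split 2:1 this gives 50 active and 25 placebo, so 50 per group with placebo pooled. One patient is 1/50 = 2% of a group.
- p_P, p_A: shares starting a drug before Week 12, assumed 5–15% on placebo and 2–6% on active.
- D: fall in Part III score when rated ON instead of OFF, assumed 6–14 points.
- f: fraction of starters rated within 12 hours of a dose.

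Shift in the active-minus-placebo difference = f × D × (p_P − p_A). With f = 1:

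| p_P | p_A | D | Shift |
|---|---|---|---|
| 0.05 | 0.02 | 6 | 0.03 × 6 = 0.18 |
| 0.10 | 0.04 | 10 | 0.06 × 10 = 0.60 |
| 0.15 | 0.06 | 14 | 0.09 × 14 = 1.26 |

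A positive shift makes the active drug look worse. Equal shares give 0, and p_A above p_P reverses the sign. The middle row means five placebo patients against two active patients (10% and 4% of 50).

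If f is 0.1 to 0.5 (also assumed), the range becomes 0.1 × 0.18 = 0.02 to 0.5 × 1.26 = 0.63, and the middle row becomes 0.06 to 0.30.

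**The case against.** The strongest reply is that the endpoint definition already excludes such a score: it applies to everyone, and a rating soon after an anti-PD dose fails it. That stands. A reader might infer that the plan permits ON ratings to count as OFF scores. The documents do not say so. What they contain is a rating table that disagrees with the endpoint, and no rule for a score that meets one and fails the other.

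Other points on that side:

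- **Few patients.** New PD drugs are prohibited, and medicated patients agree to keep their regimen. This limits the number, which is unknown. However, the plan names such medication as its intercurrent event and gives it a strategy.
- **Protocol 7.2.1 lists permitted drugs and does not define background medication.** Correct. A site could also read the words about applicability in 8.7.2 broadly and apply the interval to a new drug. The text does not tell it to.
- **Morning fasted visits make a same-morning dose unlikely.** Partly true. The rule against dosing before blood collection (Protocol 8.5) names only the investigational product and background medication. With visits recommended at 7:00 to 10:00, a dose after 19:00 to 22:00 the evening before already breaks the interval.
- **Other analyses would show it.** Supplementary Analysis 2 removes data after the event and imputes. Supplementary Analysis 1 uses the PPS, which drops major deviations affecting the primary endpoint. They partly expose the problem but do not repair the primary analysis, and neither separates correctly timed scores from mistimed ones.

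A reader might also infer that dropping a mistimed score would overturn the treatment-policy strategy. It need not. That strategy justifies keeping data after the new drug starts; it does not make a rating at the wrong interval valid. But dropping such scores as missing would move the primary analysis some way towards Supplementary Analysis 2, so the choice should be made in advance.

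**Conclusion.** The mismatch is real and lies in the primary endpoint. Its size is unknown and probably small. The 0.2 to 1.3 points is a worst case for the assumed inputs, because every starter is taken to be rated ON and more patients are taken to start on placebo. A reader might infer that the Week 12 difference will be diluted; the documents give no start rates by arm, so neither the direction nor the amount can be claimed. The trial reports nominal P-values without formal testing, so no error rate is at stake. What is at stake is a clear meaning for the primary score in the few patients whose treatment changes. The correction is worth making because it is cheap and the handling rule should not wait for data review.

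**What to change.** 1. Reconcile Protocol 1.2 (footnote 19), 8.1.1 and SAP 3.2 with the endpoint definition, so that a Part III score qualifies as the 12-hour score according to anti-PD drug use at the time of the visit, not at entry. Reconcile the pre-visit notes in Protocol 8.7 with the same definition. How newly treated patients should time their doses around a visit is a clinical matter for the sponsor and investigators; the point here is only that the passages must agree.
2. Record the time of the last anti-PD dose at each Part III rating.
3. State in the SAP, before unblinding, how a post-baseline Part III score rated less than 12 hours after any anti-PD dose is flagged and handled in the primary analysis, with a sensitivity analysis that handles it the other way.

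Cost: one added eCRF field, small wording changes in both documents, and one further sensitivity analysis. No extra visit or procedure is needed.
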